3.3 Exclusion Criteria

Subject who meets any of the following exclusion criteria prior to enrollment is not eligible for enrollment:

Prohibited Treatment or Therapies:

1. Subject has received systemic immunosuppressive therapy, including systemic corticosteroids within 14 days prior to first dose of study treatment. Subject using a physiologic replacement dose of hydrocortisone or its equivalent (defined as up to 30 mg per day of hydrocortisone or up to 10 mg per day of prednisone) or a single dose of systemic corticosteroids is eligible. Subject who received systemic steroids for asymptomatic CNS metastases within 14 days prior to first dose of study treatment is eligible.
2. Subject has received other investigational agents or devices within 28 days prior to first dose of study treatment.
3. Subject has had a prior anti-cancer mAb within 4 weeks prior to study day 1 or has not recovered (i.e., \leq grade 1 or at baseline) from AE due to mAb agents administered more than 4 weeks earlier.
4. Subject has had prior chemotherapy, targeted small molecule therapy, or radiation therapy within 2 weeks prior to study day 1 or has not recovered (i.e., \leq grade 2 or at baseline) from AEs due to a previously administered agent.

Medical History or Concurrent Disease:

5. Subject has prior severe allergic reaction or intolerance to an mAb, including humanized or chimeric antibodies that required permanent discontinuation.

6. Subject has known immediate or delayed hypersensitivity, intolerance or contraindication to any component of study treatment.
7. Subject has an active human immunodeficiency virus (HIV) infection or known active hepatitis B (HBsAg) or C infection. Subjects with well-controlled HIV infections (i.e., without detectable viral load) are eligible. For subjects who are negative for HBsAg, but HbCAb positive, an HBsAg DNA test will be performed and if positive, the subject will be excluded. Subjects with positive serology but negative hepatitis C virus (HCV) RNA test results are eligible.
8. This criterion has been removed.
9. Subject has active infection requiring systemic therapy that has not completely resolved within 14 days prior to first dose of study treatment.
10. Subject has symptomatic central nervous system (CNS) metastases and/or carcinomatous meningitis. Subject with asymptomatic CNS metastases is eligible.
11. Subject has had a major surgical procedure and has not completely recovered within 28 days prior to the first dose of study treatment.
12. Subject has psychiatric illness or social situations that would preclude study compliance, per investigator's judgment.
13. Subject has another malignancy for which treatment is required per investigator's clinical judgment. Subject with negligible risk of metastasis or death per investigator's clinical judgment is eligible (e.g., basal or squamous cell skin cancer, localized prostate cancer treated with curative intent or incidental prostate cancer T1-T2a, Gleason $\leq 3 + 4$, PSA ≤ 0.5 and who are undergoing active surveillance).
14. Subject has any concurrent disease, infection, or co-morbid condition that interferes with the ability of the subject to participate in the study, which places the subject at undue risk or complicates the interpretation of data in the opinion of the investigator.

Waivers to the exclusion criteria will **NOT** be allowed.

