1. **Screening:** The Screening period is 45 days. Re-screening may be allowed upon discussion with the medical monitor. Central laboratory results should be used to confirm eligibility, however if repeat screening labs are required, local laboratory results can be used to confirm eligibility. The screening labs used to determine eligibility should be collected within 14 days prior to C1D1. In situations where laboratory results are outside of the permitted range, the investigator may opt to retest the subject and subsequent within range central lab screening results may be used to confirm eligibility. In case of multiple central laboratory data within the Screening period, the most recent data should be used to confirm eligibility. Subjects requiring transfusions to meet eligibility criteria are not eligible. Radiologic imaging used to confirm eligibility must be conducted within 28 days prior to C1D1.
2. All subjects will be treated for a maximum of 12 cycles or until the subject meets study treatment discontinuation criteria.
3. **Study Treatment Discontinuation Visit (End of Study Treatment):** The Study Treatment Discontinuation Visit will take place ≤ 7 days following the last dose or the decision by the investigator to discontinue study treatment.
4. **30-Day Safety Follow-up Visit:** A 30-Day Safety Follow-up Visit should occur 30 days (+7 days) after the last dose of ASP1650 and will include the assessments as shown in the Schedule of Assessments above.
5. Subject must have an available tumor specimen in a tissue block or unstained serial slides, or subject is an appropriate candidate for tumor biopsy and is amenable to undergoing a tumor biopsy during the screening period. If a biopsy is performed, collection from a site other than lymph nodes is preferred. A minimum of 1 FFPE tumor tissue block with adequate viable tumor cells (preferred) OR a minimum of 9 FFPE unstained slides are required. If ≥ 9 slides cannot be provided, the sponsor should be contacted for further guidance.
6. For subjects who signed an optional ICF, an optional on-treatment tumor specimen collected ± 7 days of the C4D1 visit may be provided. A minimum of 1 FFPE tumor tissue block with adequate viable tumor cells (preferred) OR a minimum of 9 FFPE unstained slides are required. In cases where a pretreatment biopsy was performed, collection of the on-treatment specimen from the same site is preferred.

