12. Physical Exam: should include height (at Screening only), weight and ECOG performance status. All assessments should be taken predose on dosing days. A full physical exam is required at Screening. The physical exam only needs to be repeated on C1D1 if clinically significant changes from Screening are observed (in the opinion of the investigator). Targeted (symptom driven) physical exams should be conducted Q2W on day 1 of each cycle.
13. Vital signs (pulse, blood pressure, temperature) should be taken during every visit at the following time points:
 - Pre-dose at every visit
 - C1D1 and C2D1: Every 15 (\pm 5) minutes during ASP1650 infusion
 - Subsequent ASP1650 infusions: every 30 (\pm 10) minutes during ASP1650 infusions if the subject did not develop any AEs during the Post-infusion Observation Period of cycles 1 and 2. If subject develops AEs during C1D1, C2D1 or subsequent ASP1650 infusions, then collect every 15 (\pm 5) minutes during ASP1650 infusion
 - At 30 (\pm 10), 60 (\pm 10) and 120 (\pm 10) minutes post ASP1650 infusion during the Post-infusion Observation Period (for 1 or 2 hours; see footnote 10) 120 minute collection to be done only when observation period is 2 hours.
 - Unscheduled if clinically indicated
14. ECGs: a single ECG will be performed at Screening, the Study Treatment Discontinuation Visit, the 30-Day Follow-up Visit, and if clinically indicated or per local requirements. ECGs will be locally read. When collected on the same day, ECG should be collected prior to pharmacokinetic samples.
15. Imaging Assessments: Radiologic imaging will be evaluated at Screening (must be conducted within 28 days prior to C1D1) and every 6 weeks (+ 7 days) counting from C1D1 for the first 24 weeks and then every 12 weeks (\pm 7 days) thereafter until subject develops radiological disease progression per RECIST v1.1 by local investigator assessment or starts other systemic anticancer treatment, whichever comes earlier. Imaging will include CT scans with contrast of the thorax, abdomen, and pelvis. If CT scan with contrast is medically not feasible, MRI or CT scan without contrast may be used for imaging. Bone scans (or focal X-ray) or brain imaging should be performed if metastatic disease in bone or brain is suspected, respectively. The same mode of imaging should be utilized throughout the study unless medical necessity requires a change.

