3.2 Inclusion Criteria

Subject is eligible for the study if all of the following apply:

General Criteria:

1. Institutional Review Board (IRB)/Independent Ethics Committee (IEC) approved written informed consent and privacy language as per national regulations (e.g., Health Insurance Portability and Accountability Act Authorization [HIPAA] for US sites) must be obtained from the subject or legally authorized representative (if applicable) prior to any study-related procedures.
2. Subject is male and considered an adult (e.g., ≥ 18 years of age in the US) according to local regulation at the time of signing the informed consent.
3. A male subject with female partner(s) of childbearing potential must agree to use contraception as detailed in Appendix 12.3 Contraception Requirements during the treatment period and for at least 6 months after the final study drug administration.
4. Subject must not donate sperm during the treatment period and for 6 months after the final study treatment administration.
5. A male subject with a pregnant or breastfeeding partner(s) must agree to remain abstinent or use a condom for the duration of the pregnancy or time partner is breastfeeding throughout the study period and for 6 months after the final study treatment administration.
6. Subject agrees not to participate in another interventional study while receiving study drug in present study.

Disease Specific Criteria:

7. Subject has histological evidence of germ cell tumor. Subjects with seminoma and nonseminoma are eligible.
8. Subject must have a germ cell tumor that is not amenable to cure with either surgery or chemotherapy.

9. Subject must have received initial cisplatin based combination chemotherapy AND demonstrated progression following at least 1 salvage regimen for advanced germ cell neoplasm (including relapsed primary mediastinal nonseminomatous germ cell tumor).
- Initial cisplatin based combination therapy includes bleomycin-etoposide-cisplatin, cisplatin-etoposide, etoposide-ifosfamide-cisplatin or similar regimens
 - “Salvage” regimens include high dose chemotherapy, paclitaxel-ifosfamide-cisplatin, vinblastine-ifosfamide-cisplatin or similar regimens
 - “Failure” of prior therapy is defined as:
 - A > 25% increase in the products of perpendicular diameters of measurable tumor masses during prior therapy, which are not amenable to surgical resection; OR
 - The presence of new tumor that are not amenable to surgical resection; OR

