 - An increase in AFP or β hCG ($\geq 50\%$ increase in 2 separate samples collected at least 1 week apart are required if rising tumor markers are the only evidence of failure).

NOTE: Subjects with clinically growing teratoma (enlarging mature teratoma arising during or after chemotherapy for a non-seminomatous germ-cell tumor and with normal serum levels of AFP and β hCG) should undergo surgical resection if feasible.

10. Subjects with late relapse (> 2 years) not amenable to resection are eligible.
11. Subjects must have evidence of recurrent or metastatic carcinoma by 1 or more of the following:
- Subject has measurable disease according to RECIST v1.1 within 28 days prior to the first dose of study treatment. For subjects with only 1 measurable lesion and prior radiotherapy, the lesion must be outside the field of prior radiotherapy or must have documented progression following radiation therapy.
 - Subject has a baseline rising tumor marker (AFP or β hCG).

NOTE: If a rising tumor marker is the only evidence of PD, at least 2 consecutive rising values at least 1 week apart are needed. Subjects with only evidence of disease as rising tumor marker AFP and β hCG will be assessed for alternate causes of increased serum levels of these markers, such as cross reaction with luteinizing hormone (LH) (can be tested if needed by testosterone suppression of LH), hepatitis, use of marijuana or second primary tumor.

Physical or Laboratory Findings:

12. Subject must have an available tumor specimen in a tissue block or unstained serial slides, or subject is an appropriate candidate for tumor biopsy as determined by the investigator and is amenable to undergoing a tumor biopsy during the screening period.
13. Subject has ECOG performance status of 0 to 2.

14. Subject must meet all of the following criteria based on the centrally analyzed laboratory tests within 14 days prior to the first dose of study treatment. If repeat screening labs are required, local laboratory results can be used to confirm eligibility. In case of multiple central laboratory data within this period, the most recent data should be used to determine eligibility.
- Hemoglobin ≥ 8 g/dL
 - Absolute neutrophil count $\geq 1.0 \times 10^9/L$
 - Platelets $\geq 75 \times 10^9/L$
 - Albumin ≥ 2.5 g/dL
 - Total bilirubin $\leq 2 \times$ ULN or direct bilirubin \leq ULN for subjects with total bilirubin levels $> 2 \times$ ULN

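### The baseline scan may predate the last prior chemotherapy, small molecule or radiotherapy by up to about two weeks, so shrinkage from that treatment can be counted as an ASP1650 response

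*Protocol*

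**What the plan says.** Two windows before first dose are set independently.

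- **Scan.** Protocol 3.2, criterion 11, accepts a subject if "Subject has measurable disease according to RECIST v1.1 within 28 days prior to the first dose of study treatment". Table 1 footnote 1 says "Radiologic imaging used to confirm eligibility must be conducted within 28 days prior to C1D1", and footnote 15 gives the screening scan the same window.
- **Prior treatment.** Protocol 3.3, criterion 4, excludes a subject if "Subject has had prior chemotherapy, targeted small molecule therapy, or radiation therapy within 2 weeks prior to study day 1". The Synopsis and Protocol 5.1.3 repeat this.

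The neighbouring exclusions are longer and match the scan window: "Subject has had a prior anti-cancer mAb within 4 weeks prior to study day 1" (criterion 3) and "Subject has received other investigational agents or devices within 28 days prior to first dose of study treatment" (criterion 2).

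Protocol 7 defines baseline as the last observation before first dose, with no link to the end of earlier therapy. Protocol 5.7.2.2 does have a re-baselining rule, but only for biopsy: if a target lesion is biopsied after the baseline scan, a new scan should be obtained.

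The primary endpoint is confirmed ORR by modified RECIST v1.1, read by the local investigator and analysed in all enrolled subjects (Protocol 2.2.1 and 7.4.1.1; SAP 4.1 and 6.4.1). Under Protocol 7.1 the study stops at 1 or fewer responses in 13, and is called promising at 6 or more in 34.

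**The concern.** In a single-arm trial, the baseline scan is the only thing that separates the effect of the study drug from the effect of what came before. If another treatment is given after that scan and before C1D1, the change from baseline mixes the two, and the response criteria cannot tell them apart.

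The other entry rules do not close the gap:

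- Criterion 9 asks for "demonstrated progression following at least 1 salvage regimen for advanced germ cell neoplasm", not for progression after the most recent treatment.
- Criterion 11 has a radiotherapy safeguard, but it begins "For subjects with only 1 measurable lesion and prior radiotherapy, the lesion must be outside the field of prior radiotherapy" (or have progressed since). It covers subjects with one measurable lesion and says nothing about chemotherapy or small molecules.
- The requirement for two consecutive rising marker values applies only when markers are the sole evidence of disease.
- The ORR sensitivity analyses in SAP 6.4.1.3 change the response criterion, not the handling of recent therapy. The SAP also drops the per protocol set that Protocol 7.2.2 left it to define.

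Both decisions turn on small counts (2 of 13, 6 of 34), so one misattributed response can matter.

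**Working it through.** **1. The gap.** The scan may be at day -28. Criterion 4 bites only in the last 14 days. The difference is 28 - 14 = 14 days, in which treatment can follow the scan (about day -28 to day -15) without breaching any criterion.

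**2. The planned design (Protocol 7.1; SAP 3).** Inputs: n1 = 13, stop at 1 or fewer; n = 34, reject at 6 or more; null ORR 0.10, alternative 0.25.

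P(reject | p) = sum over x = 2 to 13 of P(X1 = x; 13, p) × P(X2 ≥ 6 - x; 21, p)

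- p = 0.10: 0.0957, within the stated 10%.
- p = 0.25: 0.8108, against the stated 80%.
- Probability of stopping early at p = 0.10: 0.9^13 + 13 × 0.1 × 0.9^12 = 0.621.

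The plan's figures reproduce, and a grid search confirms this as the Simon optimal design for those inputs.

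**3. One carry-over responder, true ORR 10%.** Fix one subject as a responder and leave the others at p = 0.10.

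- In stage I, the study stops only if none of the other 12 responds: 0.9^12 = 0.282, down from 0.621. Type I error becomes 0.2156.
- In stage II, type I error becomes 0.1705.

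**4. A per-subject chance of carry-over.** Let q be the chance that a true non-responder is scored as a confirmed responder because of earlier treatment. The apparent null rate is 0.10 + 0.90q. Here q = f × g, where f is the share of subjects treated between scan and C1D1, and g is the chance that such a man shows a confirmed carry-over response. The documents give neither, so every row is an assumption.

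| f | g | q | Apparent null ORR | Pass stage I | Type I error |
|---|---|---|---|---|---|
| 0 | – | 0 | 10.0% | 37.9% | 9.6% |
| 10% | 5% | 0.5% | 10.45% | 40.1% | 11.2% |
| 10% | 10% | 1% | 10.9% | 42.2% | 13.0% |
| 20% | 10% | 2% | 11.8% | 46.5% | 16.9% |

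**5. How long the shrinkage must last.** The first on-study scan is at week 6, and confirmation comes at least 4 weeks later. For treatment ending on day -15, that is about 15 + 42 + 28 = 85 days (12 weeks) at the earliest, or about 15 + 84 = 99 days (14 weeks) if confirmation waits for the scheduled week 12 scan.

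**6. With the fix.** If the scan must follow the last prior treatment, q from this route is about 0 and the planned 9.6% and 81.1% stand.

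**The case against.** The two windows do not contradict each other, and the path between them is narrow. Protocol 3.1 restricts entry to men with no standard treatment available, or ineligible for it. Such a man would have to receive other anticancer therapy after his screening scan, recover from its adverse events, and pass the laboratory criteria within 14 days of dosing. The shrinkage must then survive confirmation, and a new lesion or a confirmed marker rise of at least 50% from nadir overrides it (Protocol Table 4). SAP 6.2.3.3 lists prior therapy and radiation, and SAP 6.4.1.1 plans a swimmer plot, so individual responders could be examined. All of this stands: it makes the event uncommon and partly visible. It does not give a rule for counting it.

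A reader might infer four stronger things that the documents do not support.

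- *That the bias can run only towards a false positive.* If disease grows between the scan and C1D1 despite the interim treatment, the old scan understates the burden at dosing and can hide a response or bring progression forward. The carry-over route inflates ORR; the net effect of an outdated baseline is not known.
- *That the type I error is around 31%.* That figure needs q = 5%, for example half of all subjects treated after their scan with a 10% chance each. Nothing in the documents suggests this.
- *That the marker baseline has the same fault.* AFP and βhCG are drawn predose at every cycle (Table 1 footnote 20), and Protocol 7 takes the last value before first dose, so the C1D1 sample already serves.
- *That a freshly irradiated lesion may be chosen as a target lesion.* Lesion selection is left to RECIST v1.1, whose text is not reproduced, so this cannot be judged here.

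**Conclusion.** The concern holds as a gap in the text. The rules permit anticancer treatment after the baseline scan, and any confirmed shrinkage from it would count towards the primary ORR. The protocol already accepts the principle, since it asks for a new scan after a target-lesion biopsy.

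The size depends on a frequency that the documents do not give and that is probably low. Over an assumed q of 0.5% to 2%, type I error moves from 9.6% to between 11.2% and 16.9%. The figures of 21.6% and 17.1% are conditional on one such responder having occurred; they are not forecasts. This is a cheap improvement that protects the primary endpoint. It is not an error in the sample size, which reproduces.

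**What to change.** 1. **Protocol.** In inclusion criterion 11 (with its Synopsis copy) and Table 1 footnotes 1 and 15, require the baseline scan to be within 28 days before C1D1 and after the last dose or fraction of prior anticancer therapy; otherwise repeat it before C1D1. This is a measurement rule. The length of any washout is for the sponsor to decide.
2. **SAP 6.4.1.3.** For subjects already enrolled, add an ORR sensitivity analysis that counts as non-responders all subjects treated between their baseline scan and C1D1, and report how many there were.

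The cost of the first change is an amendment to the wording and an occasional repeat scan. The second needs only the scan date and the last prior-treatment date, assuming both are recorded. It is deliberately conservative, because a genuine responder in that group would also be counted as a non-responder, so it belongs beside the primary analysis rather than in its place.

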4 TREATMENT(S)

4.1 Identification of Investigational Product(s)

4.1.1 Study Drug(s)

ASP1650 will be supplied by Astellas as a sterile lyophilized powder preparation with the chimeric mAb ASP1650 as the active pharmaceutical ingredient.

Each vial contains 200 mg ASP1650 and has to be reconstituted with 4.4 mL sterile water for injection to a concentration of 45 mg/mL. Further dilution with sterile 5% Dextrose Injection, USP to a final concentration of 2 to 25 mg/mL according to assigned dose level is required. All excipients are animal component free and of compendial grade (European Pharmacopoeia [Ph. Eur.], current version). No preservatives are contained, since the vial is designed for single use.

The investigational product should be stored at $-20^{\circ}\text{C} \pm 5^{\circ}\text{C}$. Temperature should be controlled and monitored. Details of investigational product receipt, labeling, storage and preparation are provided in the Pharmacy Manual.

4.2 Packaging and Labeling

ASP1650 will be prepared, packaged, and labeled under the responsibility of qualified staff at APGD-Astellas US Technologies, Inc. (AUST) or sponsor's designee in accordance with APGD-AUST or sponsor's designee Standard Operating Procedures (SOPs), Good Manufacturing Practice (GMP) guidelines, ICH GCP guidelines, and applicable local laws/regulations.

The container closure system consists of a clear glass vial DIN 20R (20 mL), Ph. Eur. Hydrolytic class I, a vacuum stopper consisting of the basic polymer bromobutyl and the filler silicate and a crimping cap (aluminum). The vials carry a blue colored flip off cap.

Each carton and vial will bear a label conforming to regulatory guidelines, GMP and local laws and regulations that identifies the contents as investigational drug.

As required, a qualified person of Astellas Pharma Europe B.V. (APEBV) or sponsor's designee will perform the final release of the medication according to the requirements of the EU Directive 2003/94/EC Annex 13.

4.3 Study Drug Handling

Current ICH GCP Guidelines require the investigator to ensure that study drug deliveries from the sponsor are received by the investigator/or designee and that:

- Such deliveries are recorded,
- Study drug is handled and stored according to labeled storage conditions,
- Study drug with appropriate expiry/retest and is only dispensed to study subjects in accordance with the protocol, and
- Any unused study drug is returned to the sponsor.

Study drug inventory and accountability records will be kept by the investigator, head of study site or designee. Study drug accountability throughout the study must be documented and reconciled. The following guidelines are therefore pertinent:

- The investigator, head of study site or designee agrees not to supply study drugs to any persons except the eligible subjects in this study in accordance with the protocol.
- The investigator, head of study site or designee (i.e., study drug manager) will keep the study drugs in a pharmacy or other locked and secure storage facility under controlled storage conditions, accessible only to those authorized by the investigator to dispense these study drugs.
- A study drug inventory will be maintained by the investigator, head of study site or designee (i.e., study drug manager). The inventory will include details of material received and a clear record of when they were dispensed and to which subject.
- At the conclusion or termination of this study, the investigator, head of study site or designee (i.e., study drug manager) agrees to conduct a final drug supply inventory and

to record the results of this inventory on the Drug Accountability Record. It must be possible to reconcile delivery records with those of used and/or returned study drug. Any discrepancies must be accounted for and documented. Appropriate forms of deliveries and returns must be signed by the site staff delegated this responsibility.

- The site staff must return study drug to the sponsor or designee at the end of the study or upon expiration unless otherwise approved by the sponsor.
- Study drugs provided by Astellas will not be destroyed on-site, unless considered hazardous materials or drugs for which the clinical unit SOP dictates destruction must be handled by the institution. Destruction must not occur until final study drug accountability reconciliation has been performed and sponsor has approved destruction in writing.

